#### **4.2.1 Intraoperative Application**

The Amiodarone Hydrogel will be prepared per study protocol (see attached). CoSeal Surgical Sealant (Baxter Healthcare) consists of 2 formulations of synthetic polyethylene glycols, a dilute hydrogen chloride solution along with a sodium phosphate/sodium carbonate solution. These separate solutions are mixed at the time of application to form a hydrogel. Amiodarone hydrochloride powder (1mg/kg) will be mixed with CoSeal at the time of application to form an amiodarone containing hydrogel. The dosing of amiodarone is based on previous study using amiodarone hydrogel in post-operative coronary artery bypass patients. This hydrogel will be delivered utilizing a CO2 driver along the pulmonary vein and arterial anastomoses, and to the surface right and left atria.

#### **4.2.2 Data Collection**

Data from the prospective cohort will be collected and stored in a HIPAA compliant, encrypted and secured database. A detailed preoperative history will be obtained from the patients including: age, gender, reason for transplant, pre-transplant oxygen requirement, previous myocardial infarction, previous sternotomy, previous arrhythmia, smoking history, diabetes, stroke, hypertension. Intraoperative patient characteristics obtained will include: single lung transplant, double lung transplant, cardiopulmonary use, and ischemic time. Post-operative

patient characteristics will include: ICU duration, length of stay, post-operative atrial fibrillation during first week post-transplant, atrial fibrillation at time of discharge, atrial fibrillation at time of post-operative follow up, atrial fibrillation requiring cardioversion, atrial fibrillation requiring new anti-arrhythmic medication, asymptotic bradycardia and bradycardia requiring temporary pacemaker. Data will be collected from the subject's medical records immediately following their visits.

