	
4) Subjects willing and able to comply with the follow up requirements of the study
 
Exclusion Criteria
 
 
1) Patients with previous history of atrial fibrillation.
 
2) Patients with previously documented allergy or adverse reaction to amiodarone.
 
3) Patients with previous ablation for atrial fibrillation
 
4) Patients with an implantable pacemaker.
 
 
•

Data Collection
	
Subjects will be evaluated and enrolled for receiving the amiodarone gel during their waiting period for lung transplantation.
 
Patients who consent to be part of the study will receive the amiodarone gel during the surgery for lung transplantation. The amiodarone gel will be sprayed just after transplanting the lung(s). Patients will then be followed in-hospital until discharge and data regarding the primary study end-point will be captured.
 
Patient study visit follow-up will occur post-operatively as per standard of care after lung transplantation. Patients' follow-up is generally comprised of routine history and physical examination. These will provide sufficient data to address the secondary study end-points. All follow up data will be collected from the subject's medical records.
 
•

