#### **4.4.2 Secondary Endpoints**

- Length of Stay
- Development of post-operative atrial fibrillation during first year post transplant
- Thirty-day survival
- One-year Survival

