### **6.2.6 Follow up data collection**

Data will be collected from the subject's medical records during their standard of care visits post transplant. Standard of care visits include weekly Clinic visits for 1-month post discharge following lung transplantation. Patients will then have monthly regularly scheduled clinic appointments for the first year after transplantation.

In case the subject was already consented to participate in the study, but becomes ineligible by a change in status so that they no longer meet inclusion/exclusion criteria, the following actions will be taken.

- If study procedure/drug implant has not occurred:
- Document enrollment information (name of the study, date of consent and inclusion/exclusion) in the hospital records; complete the Enrollment and Withdrawal Forms. The form must be authorized / approved by the principal or delegated investigator.
- Inform the subject about the screen failure.
- The EC/IRB and CA should be notified appropriately about any deviations with regards to obtaining the informed consent (if applicable).

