## Post-operative Information

ICU Length of Stay (hour)

\_\_\_\_\_

Atrial Fibrillation at discharge

- Yes
- No

Treatment for A Fib

- None
- Amiodarone IV
- Amiodarone Oral
- Cardioversion (inc chemical CV)
- Rhythm device (pacemaker/ICD) placement
- Other

A Fib resolved at discharge

- Yes
- No

Bradycardia

- None
- Yes - not treated
- Yes - required pacing

Discharge Status

- Alive
- Dead

Discharge Date

\_\_\_\_\_  
(death date if patient died in hospital)

Atrila Fibrillation at 1 week

- Yes
- No

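### First-year AF is a cumulative endpoint, but the follow-up item records AF at the time of follow-up and the supplied CRF has no post-discharge AF field or onset date, so the endpoint cannot be derived from that form and may be under-counted

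*Combined protocol and SAP*

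**What the plan says.** Section 4.4.2 lists as a secondary endpoint "Development of post-operative atrial fibrillation during first year post transplant". It serves the secondary objective in 4.3.2, which concerns effectiveness over the first year.

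The data items are in 4.2.2, which describes collection for the prospective cohort. The AF items are AF in the first week, AF at discharge, "atrial fibrillation at time of post-operative follow up", and "atrial fibrillation requiring cardioversion, atrial fibrillation requiring new anti-arrhythmic medication". The last two carry no time window.

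The Data Collection row of the synopsis describes follow-up as routine history and examination, with data taken from medical records. It states: "These will provide sufficient data to address the secondary study end-points". Section 6.2.6 sets the contacts: "weekly Clinic visits for 1-month post discharge following lung transplantation", then "monthly regularly scheduled clinic appointments for the first year after transplantation". No ECG or rhythm monitoring after discharge is specified.

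The four-page CRF in Appendix E has these AF fields: AF at discharge, treatment for AF, AF resolved at discharge, and AF at 1 week. They sit with "Discharge Status" and the discharge date. None refers to the period after discharge and none is dated. Section 14.1 gives no rule for scoring first-year AF.

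**The concern.** A cumulative endpoint needs to know whether AF occurred at any time in the window. A status item answers whether AF was present on the day. The two agree for persistent AF and can disagree for an episode that starts and ends between visits.

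If interval episodes are not captured, the first-year rate moves towards the in-hospital rate, which is already the primary endpoint. Without an onset date, the post-discharge part cannot be separated from the index stay.

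The comparison is also exposed. Controls come from records and database entries (4.2), and the plan does not say how their first-year AF will be abstracted. If interval AF is found by different routes in the two groups, the difference between rates partly reflects ascertainment. Section 4.2 says this pilot is meant to supply preliminary data for a larger randomized trial, so a distorted first-year rate would carry forward.

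**Working it through.** The documents state no rate, episode length or detection probability for first-year AF, so there is no planned figure to reproduce. The check has two parts.

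**1. Can the endpoint be built from what is collected?**

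- *Follow-up item in 4.2.2:* status at follow-up, with nothing about the interval since the last contact.
- *Cardioversion and new anti-arrhythmic items in 4.2.2:* these could reveal treated interval AF. On the supplied CRF they reduce to one undated treatment field among the discharge items. AF that needed neither is not covered.
- *Adverse event review (9.2, 9.3):* records are reviewed through follow-up, with onset and resolution dates. But 9.2 sets outcome-measure results aside from adverse event capture (in the text on ancillary testing), so it is unclear whether AF would be recorded there. Under 9.3 surveillance starts after the study intervention, so historical controls have no such review.
- *Scoring:* no section says how an interval episode found in the record, or a patient with no recorded episode, counts.

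Some interval AF could therefore be found, but no field, date or rule carries it to the endpoint.

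**2. How much could visit timing matter?** This is an illustration only.

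Inputs from 6.2.6: 4 weekly visits after discharge, then monthly visits to 1 year.

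Assumptions: a month is 30.4 days; discharge is on day *d* = 14, 21 or 30; one episode of length *D* days starts at a uniformly random time between discharge and day 365; AF is scored only if present at a visit.

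For each of these *d*, 10 monthly visits fit after the weekly ones (for *d* = 21 the last is on day 21 + 28 + 10 × 30.4 = 353), giving 14 visits. The share of episodes that overlap a visit is

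[4 × min(*D*, 7) + 10 × min(*D*, 30.4)] / (365 − *d*).

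For *d* = 21 the denominator is 344:

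- 1 day: (4 + 10)/344 = 4.1%
- 3 days: (12 + 30)/344 = 12.2%
- 7 days: (28 + 70)/344 = 28.5%
- 14 days: (28 + 140)/344 = 48.8%
- 30 days: (28 + 300)/344 = 95.3%

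With *d* from 14 to 30 (denominators 351 to 335) the ranges are about 4%, 12-13%, 28-29%, 48-50% and 93-98%. The share reaches one half when 28 + 10*D* = (365 − *d*)/2, which gives *D* of about 14 to 15 days.

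Recovery from history or records changes this. If a share *q* of the missed episodes is recovered, total capture is *s* + (1 − *s*)*q*, where *s* is the visit share. Capture of one half needs *q* = (0.5 − *s*)/(1 − *s*): 48% for 1-day episodes (*s* = 0.04) and 30% for 7-day episodes (*s* = 0.29).

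**Weight of one patient.** One misclassified gel patient moves that group's rate by 1/20 = 5 percentage points. One misclassified control moves it by 1/50 = 2 points.

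**The case against.** The best defence is that 4.2.2 lists collection periods (first week, discharge, follow-up) and does not restrict the last one to rhythm on the day. A history taken at a visit normally covers the time since the last one. All follow-up data come from medical records, treated AF has its own items, and adverse events are reviewed throughout. Appendix E is not the complete form set, since the protocol names separate adverse event, death, withdrawal, deviation and study completion forms. And this is a secondary endpoint in a pilot that is not powered for it.

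Much of this stands, and it rules out several stronger readings:

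- A reader might infer that most post-discharge episodes would be scored as no AF. That needs scoring by visit status alone and episodes shorter than about 14 to 15 days. The plan states neither.
- A reader might infer that a patient cardioverted between visits would count as AF-free. Cardioverted AF is a listed item, so the documents do not support this.
- A reader might infer that no form records anything after discharge. That can be said only of the AF fields on the supplied form.
- A reader might infer that the first-year objective cannot be answered at all. The documents support possible under-counting and no more.

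The defence does not supply a field, a date or a scoring rule that connects these sources to the endpoint, nor any equivalent for the controls.

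**Conclusion.** The point holds as a mismatch between the endpoint and its data capture. First-year AF cannot be derived from the supplied CRF, and following the item in 4.2.2 literally tends to under-count it.

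The size of the under-count is not known. The visit-overlap percentages rest on assumed episode lengths, an assumed discharge day and no recovery from other sources, so they show how strongly visit timing could matter and do not estimate the loss.

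The direction of any bias between groups is also open. Adverse event review in the gel group alone would raise its AF rate relative to the controls. Full-chart abstraction for controls against visit status for gel patients would do the reverse. With 20 gel patients, one or two such cases would be visible in the result. The plan should be changed, but the primary endpoint is not affected by this point.

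**What to change.** - In 4.2.2, replace the follow-up item with: *any AF documented in the medical record since the last contact (ECG, telemetry, admission, cardioversion or new AF treatment): yes/no, date first documented*.
- Add a follow-up CRF page with this item and the date last known alive, completed at each standard-of-care visit and at 1 year.
- Abstract the same items, over the same window and from the same type of records, for the historical controls.
- Amend the Data Collection row of the synopsis so that history and examination alone are not the stated source for this endpoint.
- Optionally, once dates are recorded, show post-discharge AF separately from the index stay as a descriptive figure. Keeping the cumulative endpoint is a legitimate choice.

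The cost is one CRF page, short wording changes and extra abstraction time, mainly for the 50 controls. No visit or test is added.

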#### **4.2.3 Number of subjects required to be included in the study**

Enrollment will include at least 20 patients undergoing lung transplant. The subjects will be evaluated with the historic controls (50).

#### **4.2.4 Estimated time needed to enroll this subject population**

Enrollment is expected to occur over a 24-month period with the total duration of the study continuing up to 30 months, dependent on the rate of enrollment and the regulatory timeline.

### **4.3 OBJECTIVES**

#### **4.3.1 Primary Objective**

Demonstrate safety and effectiveness of the amiodarone hydrogel application during lung transplantation in preventing atrial arrhythmias during index hospital stay.

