## 1.0 SYNOPSIS

Title:	The Intra-Operative Application of Amiodarone Releasing Hydrogel to Prevent Postoperative Atrial Fibrillation in Patients Undergoing Lung Transplantation
Acronym:	AMGeL
Purpose:	The purpose of the study is to evaluate the intraoperative application of an amiodarone containing hydrogel for prevention of post-operative atrial fibrillation in lung transplant patients.
Objectives:	
Primary Objective: The purpose of the study is to evaluate the intraoperative application of an amiodarone containing hydrogel for prevention of post-operative atrial fibrillation in lung transplant patients.
 
Secondary Objective: Demonstrate safety and effectiveness of the amiodarone hydrogel application during lung transplantation in preventing atrial arrhythmias during first year of transplantation.

Endpoints:	
Primary Endpoint will evaluate: --Development of post-operative atrial fibrillation during initial hospitalization
 
Secondary Endpoints to be evaluated: --Length of Stay initial hospital stay -Development of post-operative atrial fibrillation during first year post transplant -Thirty-day survival -One-year Survival

Design:	
In Lung Transplant patients, we propose use of amiodarone hydrogel during surgery will result in reduced rates of post-op atrial fibrillation.
 
The expected total duration of the study is 24 months.
 
The clinical study will be conducted in 1 center in the United States.
 
20 subjects will be enrolled in this study.
 
The enrolled subjects will be compared to the historical controls who did not receive the amiodarone gel therapy during lung transplant surgery.
 
Subjects will be followed for 1 year.

Drug used:	Amiodarone Hydrogel in Coseal
Study Population	Male and female patients, age 18 years and older with end stage Lung Disease who require Lung Transplant.
Inclusion/Exclusion Criteria	
Inclusion Criteria
 
 
1) Subject or legal representative has signed Informed Consent Form (ICF)
 
2) Undergoing lung transplant at the Jewish Hospital
 
3) Age <math>\geq</math> 18 years
 

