### **4.4. ENDPOINTS**

#### **4.4.1 Primary Endpoint**

-Development of post-operative atrial fibrillation during initial hospitalization

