## 14.0 STATISTICAL CONSIDERATIONS

### 14.1 STATISTICAL DESIGN, HYPOTHESES, METHOD AND ANALYTICAL PROCEDURES

This clinical study will provide data to support the safety, preliminary efficacy, and performance of the use of the Amiodarone hydrogel in preventing atrial arrhythmia during lung transplantation. The study has a treatment arm and a control arm. The control arm is the historic controls and will use the previously treated lung transplant patients at the facility. The treatment arm will use investigational amiodarone hydrogel. The study sample size calculation is based on typical regulatory criteria for a feasibility study to assess for safety and preliminary effectiveness hence it is not based on a power analysis to show statistically significant difference between the groups. However, the reported rate of early atrial fibrillation post lung transplantation is approximately 30% and assuming that the use of amiodarone gel will result in prevention of atrial fibrillation in 90% patients a sample size of 20 in each arm may have sufficient power to answer the question of preliminary effectiveness and safety.

Endpoint analysis will be on “as-treated” basis as historical control data will be used. Patients who will dropout or withdraw from the study before reaching the primary end-point will be excluded from the study and replaced by new enrollees to have at least 20 patients enrolled the study arm. The primary end-point analysis will be based on the study groups as per the protocol (treatment group vs. control groups). Subjects, who withdraw consent, will not be included in analyses.

All clinically relevant baseline and follow up variables will be tabulated. Means, medians, proportions and 95% confidence intervals will be reported. Comparisons of data collected at baseline and at follow-up will be analyzed as follows: categorical variables will be tested using contingency tables analyses (exact or chi-square approximations), and continuous variables will be tested using unpaired Student’s t-test or Wilcoxon rank-sum test, depending on variable distribution. The post-transplant AFIB was evaluated between study and control groups for overall occurrence, AFIB lasting < 24 hours and AFIB lasting > 24 hours. All the data were analyzed using SAS 9.4 software (SAS Inc., Cary, NC).

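### Sections 4.3.1 and 4.3.2 aim to demonstrate safety, but no safety criterion is set, and even zero events in 20 patients would not exclude a harm rate of 13.9% (one-sided) or 16.8% (two-sided).

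*Combined protocol and SAP*

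**What the plan says.** The primary objective in section 4.3.1 is: "Demonstrate safety and effectiveness of the amiodarone hydrogel application during lung transplantation", with the index hospital stay as the time frame. Section 4.3.2 uses the same verb for the first year, and section 3.2 also anticipates showing that the treatment is safe and effective. The synopsis differs. Its primary objective reads "Primary Objective: The purpose of the study is to evaluate the intraoperative application of an amiodarone containing hydrogel for prevention of post-operative atrial fibrillation" and does not name safety, although its secondary objective does.

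The only primary endpoint (4.4.1) is "Development of post-operative atrial fibrillation during initial hospitalization". Among the secondary endpoints in 4.4.2, "Thirty-day survival" and one-year survival bear on safety. The others are length of stay and first-year AF.

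Section 14.1 says the size follows feasibility criteria and was not derived from a power calculation for a group difference. It then says that "a sample size of 20 in each arm may have sufficient power to answer the question of preliminary effectiveness and safety". The rates that it supplies are an AF rate of about 30% and prevention of AF in 90% of patients.

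Safety data are collected. Section 4.2.2 lists bradycardia with and without temporary pacing, the case report form has the option "Yes - required pacing", and section 9.3 records all adverse events and deaths.

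**The concern.** To demonstrate safety, a study must be able to rule out some unacceptable rate of harm. That needs a named outcome, a limit and enough patients to exclude the limit. The plan gives neither a limit nor a designated outcome, and its power sentence extends to safety without any safety input. Bradycardia, the harm that section 3.3.1 links to the gel on the basis of the earlier bypass surgery study, is recorded but is not an endpoint.

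Section 4.2 says the data are to support a larger randomised trial. A small number of events, or none, could be taken as meeting the stated objective even though the data remain compatible with a substantial harm rate.

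**Working it through.** **1. The plan's own figure, 20 per arm.** Section 14.1 states no alpha or power, so alpha 0.05 and 80% power are assumed here. With pooled variance, n per arm = [z(alpha) × √(2·p̄·(1−p̄)) + z(beta) × √(p1(1−p1) + p2(1−p2))]² / (p1−p2)².
- AF 30% v 10% (90% of treated patients free of AF), two-sided: (1.96 × √0.32 + 0.842 × √0.30)² / 0.20² gives 62 per arm; one-sided gives 49. Power at 20 per arm is 35% two-sided by this approximation and 24% by Fisher's test.
- AF 30% v 3% (a 90% relative reduction): 29 per arm two-sided, 23 one-sided. Power at 20 per arm is 64% two-sided by this approximation and 56% by Fisher's test.

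So 20 per arm does not follow from the rates in 14.1 under these assumptions, which fits the section's own statement that it was not derived from a power analysis. The safety part cannot be reproduced at all, because there is no harm rate or margin to enter.

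**2. What 20 treated patients can exclude.** For x events in n patients, the exact (Clopper-Pearson) upper limit is the 1−a quantile of Beta(x+1, n−x), with a = 0.05 one-sided or 0.025 two-sided. For x = 0 it reduces to 1 − a^(1/n).
- 0/20: 1 − 0.05^(1/20) = 13.9% one-sided; 1 − 0.025^(1/20) = 16.8% two-sided.
- 1/20: 21.6% one-sided; 24.9% two-sided.
- 2/20: 28.3% one-sided; 31.7% two-sided.

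Zero events is the best case; each observed event raises the limit. Setting (1−p)^n ≤ a, excluding a 10% rate with zero events would take 29 patients (one-sided) or 36 (two-sided). Excluding 5% would take 59 or 72.

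**3. Chance of seeing no event at all.** P(0 of 20) = (1−p)^20.
- True rate 5% (assumed): 0.95^20 = 0.358, or 36%.
- True rate 10%: 0.90^20 = 0.122, or 12%. Section 3.3.1 reports transient, non-serious bradycardia in more than 10% of patients in the earlier study. That is the only rate in the documents for a harm linked to the gel.

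**4. Power to detect an excess over controls.** The documents give no harm rates for the two groups, so these pairs are illustrative assumptions. Power is the sum of binomial probabilities over all outcome pairs with a two-sided Fisher p-value of 0.05 or less. Both allocations are shown because 14.1 speaks of 20 in each arm and 4.2.3 of 50 historical controls.

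| Harm rate, gel v control | 20 v 20 | 20 v 50 |
|---|---|---|
| 15% v 5% | 7% | 21% |
| 20% v 5% | 17% | 39% |

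**The case against.** The strongest reply is that the plan is modest about itself. Section 4.2 calls it a pilot, and 14.1 sizes it on feasibility criteria, says only that power may be sufficient, and speaks of preliminary effectiveness and safety. That stands, and it means 20 patients is not in itself a defect. It does not rescue the verb in 4.3.1 and 4.3.2, because a pilot is suited to describing safety rather than demonstrating it.

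A reader might infer four stronger criticisms that the documents do not support.
- *There is no safety endpoint.* Thirty-day and one-year survival are listed. What is missing is a primary or designated safety endpoint and any bradycardia or adverse event endpoint.
- *There is no safety analysis.* Section 14.1 promises to tabulate all clinically relevant follow-up variables, with proportions, 95% confidence intervals and tests for categorical data. This can cover the bradycardia items, although nothing commits to using them to judge safety.
- *Safety would be declared from an adverse event listing.* No section says so, and sections 9.2 and 9.3 set out grading of severity, seriousness and causality.
- *The plan asserts adequate power for safety.* It says only that power may be sufficient.

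The choice of safety outcome is also partly a matter of judgement, since section 3.3.1 discusses tissue damage and systemic effects as well as bradycardia.

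**Conclusion.** The point holds as a mismatch between the stated objective and what the design can deliver. The plan sets out to demonstrate safety and mentions power for it, without a harm rate, an acceptable limit or a designated safety endpoint, and the synopsis primary objective does not match 4.3.1. The limits of 13.9% and 16.8% depend on seeing no events among exactly 20 treated patients; they are not a general bound on what the study will show. They need no assumption about control rates. The power figures of 7% to 39% do rest on assumed harm rates and a two-sided 0.05 Fisher test, and serve only as illustration. The wording should be corrected; the findings here do not call for a larger sample.

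**What to change.** - In 4.3.1 and 4.3.2, change the aim to describing safety and estimating the effect. Bring the synopsis objectives into line, and section 3.2 with them.
- In 14.1, remove safety from the sufficient-power sentence and state the precision instead: with 20 treated patients, the two-sided 95% exact upper limit is 16.8% for 0 events and 24.9% for 1.
- Name the bradycardia items already collected, including bradycardia requiring pacing, as a designated safety outcome. Report it with an exact 95% confidence interval, alongside the control rate where the historical records allow.

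The cost is protocol and SAP wording plus one table. No extra patients are needed, and no new case report form item for treated patients. The control rate depends on what the records hold. The downside is a less favourable stated claim.
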